7.7.2 Laboratory Tests

Clinical laboratory assessments for this study include: hematology, blood chemistry and liver function tests (LFT). Most hematology, blood chemistry and LFT parameters will be graded according to NCI-CTCAE version 4.03, as applicable. Numeric values will be analyzed after conversion into standard international units, where applicable. A complete listing of all laboratory parameters with normal ranges in standard international units is included in Appendix 5. Laboratory values with grade 3 or above will be listed. For subjects with grade 3 or higher values, all values of that lab test will be listed.

Continuous clinical laboratory results will be summarized by analyte and by visit after conversion into standardized SI results. Summary statistics for the change from baseline to end-of-treatment (EOT), where end-of-treatment will be summarized using the last non-missing post-baseline result no more than 45 days after treatment discontinuation or initiation of subsequent therapy (whichever is first, if applicable), will be tabulated. The largest change from baseline (increase or decrease) will be summarized in a shift table based on the CTCAE grade which will include both scheduled and unscheduled visits.

Laboratory-based summaries will be provided as follows:

- Observed, change from baseline, and percent change from baseline at each scheduled visit and EOT in parameter results

- Shift from baseline to maximum post-baseline CTCAE grade for hematology laboratory results
- Shift from baseline to maximum post-baseline CTCAE grade for chemistry laboratory results
- Elevations in AST, ALT, total bilirubin, and alkaline phosphatase as outlined in the FDA Guidance for Industry pertaining to premarketing clinical evaluations for drug-induced liver injury (DILI):
 - Elevations of AST, ALT, and either ALT or AST: 3x-, 5x-, 10x-, and 20xULN
 - Elevations of bilirubin defined as total bilirubin >2 xULN
 - Elevations of alkaline phosphatase >1.5 xULN
 - Elevations of ALT or AST (>3 xULN) accompanied by elevated total bilirubin (>1.5 xULN, >2 xULN)

In addition, a listing of potential Hy's Law cases (i.e., subjects with AST or ALT >3 xULN in combination with bilirubin >2 xULN) will be also presented. Results from unscheduled or repeated assessments will be included in the DILI evaluations, with elevations of AST or ALT in combination with total bilirubin at the same unscheduled or repeat assessment.

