9.2.9.3 Other Safety Analyses

Vital Signs

Summary statistics and change from baseline and/or pre-dose to post-dose may be tabulated where appropriate.

ECOG Status

ECOG status will be summarized for each visit. Shifts from baseline to the best and worst post-baseline score may be tabulated.

Clinical Laboratory Results

Summary statistics of laboratory results and change from baseline to scheduled post-baseline visits may be tabulated as appropriate.. Directional shifts in laboratory toxicity grades per NCI CTCAE v4.03 will be analyzed using standard shift tables. Shift tables will present directional shifts from baseline to above or below the laboratory standard normal range. . Laboratory values will be listed with grade per NCI CTCAE, v4.03 and out of the normal range flags.

Electrocardiogram

ECG status (normal, abnormal clinically significant, or abnormal not clinically significant) will be summarized for each scheduled ECG, and shifts from baseline may be tabulated. Summary statistics of each ECG parameter results and change from baseline to scheduled post-baseline visits may be tabulated as appropriate.

In addition, mean, median and maximum absolute change from baseline of QTcF will be assessed and summarized, where $QTcF = \frac{QT}{\sqrt[3]{RR}}$.

Categorical outliers (e.g. QTcF > 450 msec, > 480 msec, and > 500 msec or $\Delta QTcF$ from baseline > 30 msec and > 60 msec) will be presented.

The relationship between plasma concentration of study drug and SC-DR002 with $\Delta QTcF$ will be assessed and described with an appropriate model. Details will be provided in the SAP.

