9. VISIT WINDOWS

Efficacy analyses based on response assessment will include all scans, including those from unscheduled visits. All data will be tabulated according to scheduled visits, unless otherwise specified. No visit windows will be developed for the safety analysis of this study. Unscheduled visits will be used to determine baseline, the last post-baseline value, maximum change from baseline in shift tables, or determination of response.

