TABLE 14.3_2.8.4 Incidence of Treatment-Emergent Drug-Related Serious Adverse Events by System Organ Class, Preferred Term, and Gender During Initial Treatment

TABLE 14.3_2.8.5 Incidence of Treatment-Emergent Adverse Events Leading to Study Drug Discontinuation by System Organ Class, Preferred Term, and Gender During Initial Treatment

TABLE 14.3_2.8.6 Incidence of Treatment-Emergent Adverse Events Leading to Death by System Organ Class, Preferred Term, and Gender During Initial Treatment

TABLE 14.3_2.9.1 Incidence of Treatment-Emergent Adverse Events by System Organ Class, Preferred Term, and Age Group During Initial Treatment

TABLE 14.3_2.9.2 Incidence of Treatment-Emergent Serious Adverse Events by System Organ Class, Preferred Term, and Age Group During Initial Treatment

TABLE 14.3_2.9.3 Incidence of Treatment-Emergent Drug-Related Adverse Events by System Organ Class, Preferred Term, and Age Group During Initial Treatment

TABLE 14.3_2.9.4 Incidence of Treatment-Emergent Drug-Related Serious Adverse Events by System Organ Class, Preferred Term, and Age Group During Initial Treatment

TABLE 14.3_2.9.5 Incidence of Treatment-Emergent Adverse Events Leading to Study Drug Discontinuation by System Organ Class, Preferred Term, and Age Group During Initial Treatment

TABLE 14.3_2.9.6 Incidence of Treatment-Emergent Adverse Events Leading to Death by System Organ Class, Preferred Term, and Age Group During Initial Treatment

TABLE 14.4_1.1 Chemistry: Observed and Change from Baseline During Initial Treatment

TABLE 14.4_1.2 Chemistry: Shift from Baseline to Maximum Post-Baseline NCI-CTCAE Grade During Initial Treatment

TABLE 14.4_2.1 Hematology: Observed and Change from Baseline During Initial Treatment

TABLE 14.4_2.2 Hematology: Shift from Baseline to Maximum Post-Baseline NCI-CTCAE Grade During Initial Treatment

TABLE 14.4_3.1 Coagulation: Observed and Change from Baseline During Initial Treatment

TABLE 14.4_3.2 Coagulation: Shift from Baseline to Maximum Post-Baseline NCI-CTCAE Grade During Initial Treatment

TABLE 14.4_4.1 Elevated AST, ALT, Total Bilirubin, and Alkaline Phosphatase During Initial Treatment

TABLE 14.3_5.1 Vital Signs During Initial Treatment

TABLE 14.3_5.2 Electrocardiogram During Initial Treatment

TABLE 14.3_6.1 Electrocardiogram: Summary of QTcF1 Interval During Initial Treatment

TABLE 14.3_7.1 Echocardiography: Pericardial Effusion During Initial Treatment

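### SAP 7.7.2 gives two conflicting rules for the laboratory shift tables, largest change from baseline and maximum post-baseline CTCAE grade, and makes no provision for direction

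*SAP*

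**What the plan says.** The SAP describes the laboratory shift tables in four places.

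- **SAP 7.7.2, narrative:** "The largest change from baseline (increase or decrease) will be summarized in a shift table based on the CTCAE grade". The sentence goes on to include scheduled and unscheduled visits.
- **SAP 7.7.2, bullets just below it:** "Shift from baseline to maximum post-baseline CTCAE grade for hematology laboratory results" and "Shift from baseline to maximum post-baseline CTCAE grade for chemistry laboratory results".
- **SAP Appendix G, table titles:** Table 14.4_2.2 is "Hematology: Shift from Baseline to Maximum Post-Baseline NCI-CTCAE Grade During Initial Treatment" and Table 14.4_1.2 is "Chemistry: Shift from Baseline to Maximum Post-Baseline NCI-CTCAE Grade During Initial Treatment". Table 14.4_3.2 has the same form for coagulation.
- **SAP 9:** data are tabulated by scheduled visit unless otherwise specified. Unscheduled visits may be used for a short list of purposes, one of which is "maximum change from baseline in shift tables".

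SAP 7.7.2 also plans a listing of values of Grade 3 or above, and adds: "For subjects with grade 3 or higher values, all values of that lab test will be listed".

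Protocol 9.2.9.3 says: "Directional shifts in laboratory toxicity grades per NCI CTCAE v4.03 will be analyzed using standard shift tables". It also asks for shifts from baseline to above or below the normal range.

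**The concern.** A shift table needs one rule for choosing the post-baseline record. Largest change and maximum grade are different rules, and the SAP attaches both to the same tables. Under the first, a recovery value can displace the nadir, so a severe cytopenia may be shown as normal.

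The affected tests matter in this trial. Protocol 1.1.3 names thrombocytopenia among the notable toxicities, and Protocol 5.5.1 monitors hypoalbuminemia. Table 5-3 recommends growth factors for neutropenia, so a neutrophil count that rises above baseline after a nadir is plausible.

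The protocol also asks for directional shifts. Neither SAP rule says how low and high abnormalities of the same test are to be separated.

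**Working it through.** No figure in the plan depends on this rule, so there is none to reproduce. The check applies each rule to the same values.

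**Inputs**
- Grades (Protocol Appendix 12.5): platelets below 25 × 10^9/L are Grade 4; neutrophils (ANC) below 0.5 × 10^9/L are Grade 4; albumin below 3 to 2 g/dL is Grade 2 and below 2 g/dL is Grade 3.
- Normal ranges (SAP Appendix E): platelets 150–350, neutrophils 1.8–7.8, albumin 3.5–5 g/dL.
- Floors: platelets 75 and ANC 1.5 at entry (Protocol 4.1); platelets 75 and ANC 1.0 on each dosing day (Protocol 5.2.2). There is no entry limit for albumin.
- The subject courses below are illustrative assumptions.

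**Reading 1: largest change in raw value.** Let B be baseline, m the nadir and v a later value. The fall is B − m and the rise is v − B. The later value is selected when v − B > B − m, that is, when v > 2B − m.

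| Test | B, m, v | 2B − m | Changes | Grade shown |
|---|---|---|---|---|
| Platelets | 100, 20, 200 | 180 | −80, +100 | 0 |
| Platelets | 150, 20, 250 | 280 | −130, +100 | 4 |
| Platelets | 250, 20, 250 | 480 | −230, 0 | 4 |
| ANC | 2.0, 0.3, 5.0 | 3.7 | −1.7, +3.0 | 0 |
| ANC | 5.0, 0.3, 5.0 | 9.7 | −4.7, 0 | 4 |

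For ANC with B = 2.5 and m = 0.4, the threshold is 5.0 − 0.4 = 4.6, so any later value from just above 4.6 up to 7.8 is normal and hides the Grade 4.

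Limits of the effect:
- If v = B, the condition becomes m > B, which is impossible after a fall. Recovery only to baseline never masks.
- With recovery inside the normal range, masking a Grade 4 platelet nadir needs B below about (350 + 25)/2 = 187.5. For ANC it needs B below about (7.8 + 0.5)/2 = 4.15.
- With a platelet nadir of 20 and B below (150 + 20)/2 = 85, every recovery to 150 or more masks.

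**Reading 2: largest change in CTCAE grade.** A platelet baseline of at least 75 is at most Grade 1, so recovery to Grade 0 is a change of at most −1. A fall from Grade 1 to Grade 3 or 4 is +2 or +3, so a severe platelet nadir cannot be masked. A grid of 16,072 platelet combinations (baseline 75–350, nadir below 25, recovery 150–350) agrees: none is masked on this reading, against 3,331 on Reading 1. These counts describe the grid and are not estimates of frequency.

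Albumin can be masked. Values of 2.8, then 3.6, then 1.9 g/dL are Grades 2, 0 and 3. The grade changes are −2 and +1, so the rule selects 3.6 and shows Grade 0. On Reading 1 the raw changes are +0.8 and −0.9, so it selects 1.9 and shows Grade 3. The two readings of the one sentence therefore disagree with each other as well.

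**Reading 3: maximum post-baseline grade.** Every course in the table shows Grade 4, and the albumin course shows Grade 3.

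**Unscheduled values.** The bullets and table titles do not mention them. For the shift tables, unscheduled values are admitted only by the narrative sentence in 7.7.2 and the phrase in SAP 9. Within a cycle, blood counts are scheduled on Days 1, 15 and 29 (Protocol 6.3), so a nadir may be seen only on an unscheduled draw. Deleting the narrative sentence without replacing it would weaken the case for using that value.

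**Direction.** No SAP text or Appendix G title separates low from high. Appendix E gives both a lower and an upper limit for tests such as sodium, potassium and glucose. If such a test is graded in both directions, one maximum grade per subject does not show which direction produced it.

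**The case against.** A reader might infer that the SAP uses largest change in place of worst grade, so that Grade 4 nadirs will appear as Grade 0. The documents do not support that. The list introduced as the summaries to be provided, and the three Appendix G titles, specify maximum grade. Appendix G plans no laboratory table of largest change. If those texts govern and all values are used, the nadir is shown.

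Other points on this side also stand:
- Values of Grade 3 or above are listed with all results for that test. Clinically significant abnormalities are reported as adverse events (Protocol 7.6.1.6), where the most severe occurrence is counted (SAP 7.7.1). A listing is not an incidence table, but the events are not lost.
- Masking on the raw-value reading needs a rise above baseline larger than the fall. No document says platelets overshoot baseline, and Table 5-3 recommends growth factors for neutropenia only. How often this would happen is unknown.
- The sentence refers to the CTCAE grade, so the grade-change reading is open, and on that reading platelets are safe. ANC is nearly so: only a Day 1 baseline between 1.0 and 1.5 is Grade 2. From there a later Grade 3 could be masked by recovery to Grade 0, and a Grade 4 would tie at two grades each way.
- The SAP 9 sentence lists uses of unscheduled visits. It echoes the rule more than it sets one.
- The wording on increase or decrease could be meant to cover each direction in turn. Table layouts are not shown, so it cannot be said that low and high will be merged.

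These points limit the harm. They do not remove the conflict: nothing says which text prevails, and the narrative sentence also carries the instruction on unscheduled values.

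**Conclusion.** The point holds as a conflict between two record-selection rules for the same safety tables. One of them can give a wrong grade on either reading: on raw values, Grade 0 after a Grade 4 nadir when v > 2B − m; on grades, Grade 0 for a Grade 2, 0, 3 course. A programmer and a checker could each follow a different SAP sentence and get different tables.

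The size in subjects cannot be estimated from the documents. It is zero if the maximum-grade texts are followed with all values included. The worked courses rest on assumed subject values; only the cut-offs, ranges and floors come from the documents.

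Separately, the SAP has no stated provision for the directional shifts in protocol 9.2.9.3. Which tests are graded both ways must be taken from CTCAE v4.03, since Protocol Appendix 12.5 gives laboratory grades only for albumin, neutrophils and platelets.

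**What to change.** - In SAP 7.7.2, replace the largest-change sentence with: for each test, the table shows the shift from baseline grade to the worst (highest) post-baseline CTCAE grade, using all scheduled and unscheduled values in the period.
- In SAP 9, replace the matching phrase on maximum change with worst post-baseline grade in shift tables.
- State that tests graded in both directions are tabulated separately for low and high, and carry this into Tables 14.4_1.2, 14.4_2.2 and 14.4_3.2 where it applies.

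The cost is two sentences and a few table rows. The Appendix G titles already fit the corrected rule, and no data collection changes.

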4.1 Inclusion Criteria

1. Adult aged 18 years or older
2. Histologically confirmed small-cell lung cancer (SCLC) with documented disease progression after at least 2 prior systemic regimens, including at least one platinum-based regimen
3. DLL3-expressing SCLC based on central immunohistochemistry (IHC) assessment of banked or otherwise representative tumor tissue.
4. Measurable disease, defined as at least 1 tumor lesion ≥ 10 mm in the longest diameter or a lymph node ≥ 15 mm in short-axis measurement assessed by CT scan (RECIST v1.1)
5. Eastern Cooperative Oncology Group (ECOG) performance status of 0 or 1. See Appendix 12.2 for conversion of performance status using Karnofsky scales, if applicable
6. Minimum life expectancy of at least 12 weeks
7. Subjects with a history of central nervous system (CNS) metastases must have documentation of stable or improved status based on brain imaging for at least 2 weeks after completion of definitive treatment and within 2 weeks prior to first dose of Study Drug, off or on a stable dose of corticosteroids. Definitive treatment may include surgical resection, whole brain irradiation, and/or stereotactic radiation therapy
8. Recovery to Grade 1 of any clinically significant toxicity (excluding alopecia) prior to initiation of study drug administration
9. Satisfactory laboratory parameters:
 - a. Absolute neutrophil count (ANC) $\geq 1,500/\mu\text{L}$
 - b. Platelet count $\geq 75,000/\mu\text{L}$

- c. Hemoglobin \geq 8.0 g/dL
- d. Serum total bilirubin \leq 1.5x upper limit of normal (ULN) or \leq 3x ULN for subjects with Gilbert's disease
- e. Serum alanine aminotransferase (ALT) and aspartate aminotransferase (AST) \leq 2.5x ULN (\leq 5x ULN if evidence of hepatic involvement by malignant disease)
- f. Serum creatinine \leq 1.5x ULN or estimated glomerular filtration rate (eGFR) \geq 30 mL/min/1.73 m² as calculated by the 4-variable Modification of Diet in Renal Disease (MDRD) study equation (GFR (mL/min/1.73 m²) = 175 \times (serum creatinine [mg/dL]) $-1.154 \times$ (age [years]) -0.203×0.742 (if female) $\times 1.212$ (if African American; [Levey, 2006](#))

10. Last dose of any prior therapy administered by the following time intervals before the first dose of study drug:

- a. Chemotherapy, small molecule inhibitors, radiation, and/or other investigational anticancer agents (excluding investigational monoclonal antibodies): 2 weeks

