7.6.1.7 Potential Drug-Induced Liver Injury

Wherever possible, timely confirmation of initial liver-related laboratory abnormalities should occur prior to reporting a potential drug-induced liver injury (DILI) event ([FDA 2009](#)). All occurrences of potential DILIs, meeting the defined criteria, must be reported as SAEs.

Potential drug-induced liver injury is defined as:

- ALT or AST elevation > 3 times (3X) upper limit of normal (ULN); AND
- Total bilirubin > 2X ULN, without initial findings of cholestasis (elevated serum alkaline phosphatase), AND
- No other immediately apparent possible causes of aminotransferase (AT) elevation and hyperbilirubinemia, including, but not limited to, viral hepatitis, pre-existing chronic or acute liver disease or tumor(s), or the administration of other drug(s) known to be hepatotoxic

In general, an increase of serum AT to > 3X ULN should be followed by repeat testing within 48-72 hours of all four of the usual serum measures (ALT, AST, alkaline phosphatase, and total bilirubin) to confirm the abnormalities and to determine if they are increasing or decreasing.

Inquiry regarding symptoms should also be made (e.g., fatigue, nausea, vomiting, right upper quadrant pain or tenderness, fever, rash). Subjects may be retested locally, but normal laboratory ranges should be recorded and results made available to the investigator immediately for review. All data must be recorded on the case report forms. Close observation should be initiated if symptoms persist or repeat testing shows AT >3xULN for subjects with normal baseline

measures or 2-fold increases above baseline values for subjects with elevated values before drug exposure. If close monitoring is not possible, study drug should be discontinued.

Close observation includes:

- Repeating liver enzyme and serum bilirubin tests two or three times weekly. Frequency of retesting can decrease to once a week or less if abnormalities stabilize or the study drug has been discontinued and the subject is asymptomatic.
- Obtaining a more detailed history of symptoms and prior or concurrent diseases.
- Obtaining a history of concomitant drug use (including non-prescription medications and herbal and dietary supplement preparations), alcohol use, recreational drug use, and special diets.
- Ruling out acute viral hepatitis types A, B, C, D, and E; autoimmune or alcoholic hepatitis; NASH; hypoxic/ischemic hepatopathy; and biliary tract disease.

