7.7.4 Analyses of ECG Change

ECG parameter will be summarized by test and by visit. Summary statistics for the change from baseline at end-of-treatment (EOT), where end-of-treatment will be summarized using the last non-missing post-baseline result no more than 45 days after treatment discontinuation or initiation of subsequent therapy (whichever is first, if applicable), will be tabulated. In the case of multiple assessments at a visit, baseline will

be the last value prior to dosing. Observed values, change from baseline, and percent change from baseline at each scheduled visit and EOT in parameter results will be summarized. One-sided 95% confidence interval for the change from baseline will be provided for each visit.

The QTcF triplicate will be summarized and tabulated by maximum QTcF (msec) increase from baseline and QTcF (msec) value at any time during treatment:

- Maximum QTcF (msec) increase from baseline on treatment:
 - $\Delta\text{QTcF} > 10$ msec
 - $\Delta\text{QTcF} > 20$ msec
 - $\Delta\text{QTcF} > 30$ msec
 - $\Delta\text{QTcF} > 60$ msec
- QTcF on treatment:
 - $\text{QTcF} > 450$ msec
 - $\text{QTcF} > 480$ msec
 - $\text{QTcF} > 500$ msec

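### Liver-test and absolute QTcF threshold counts carry no baseline condition, so some subjects already over a limit before dosing can be counted

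*SAP*

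**What the plan says.** SAP 7.7.2 (Laboratory Tests) defines its liver categories as multiples of the ULN:

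- for the aminotransferases, "Elevations of AST, ALT, and either ALT or AST: 3x-, 5x-, 10x-, and 20xULN"
- for bilirubin, a single row at more than 2x
- for alkaline phosphatase, a single row at more than 1.5x
- for the combination, ALT or AST above 3x together with total bilirubin above 1.5x or above 2x, and a listing of potential Hy's Law cases (3x with 2x).

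SAP 7.7.4 tabulates QTcF in two ways: by the largest increase from baseline (above 10, 20, 30 and 60 msec), and by "QTcF (msec) value at any time during treatment" (above 450, 480 and 500 msec). The liver rows and the absolute QTcF rows have no baseline condition.

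Protocol 4.1, criterion 9, caps AST and ALT at 2.5x ULN, relaxed to "5x ULN if evidence of hepatic involvement by malignant disease". It caps total bilirubin at 1.5x ULN, or "3x ULN for subjects with Gilbert's disease". Neither Protocol 4.1 nor 4.2 limits alkaline phosphatase or the QTc interval.

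SAP Section 6 defines the Initial Treatment Period by when it ends (retreatment, new anticancer therapy or end of study) and gives no starting point. Table 14.4_4.1 (liver elevations) and Appendix 16.2_8.1 (potential Hy's Law cases) cover that period.

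**The concern.** An eligible subject with liver involvement can start at 4x ULN, stay at 4x throughout, and be counted as an AST/ALT elevation during treatment. A subject with a long QTcF before the first infusion can be counted in the same way. Because the period definition does not rule out pre-dose values, the liver rows could even be met by a baseline measurement alone. For QTcF that reading is less likely, because SAP 7.7.4 labels those rows as on treatment.

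The threshold tables are where a reader will look first for a liver or QT signal. There is no control arm to show the background rate, so values that were high beforehand and values that became high on drug appear as one percentage. The bias runs upward in every affected row.

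**Working it through.** **1. Entry limits against thresholds.** This assumes that entry and analysis use the same ULN and that the baseline value lies within the entry limit.

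| SAP row | Entry limit | Can it be exceeded at entry? |
|---|---|---|
| AST/ALT 3x | 2.5x; 5x with hepatic involvement | Only with hepatic involvement (2.5 < 3 < 5) |
| AST/ALT 5x, 10x, 20x | as above | No; 5x is the ceiling |
| Bilirubin >2x | 1.5x; 3x with Gilbert's | Only with Gilbert's (1.5 < 2 < 3) |
| Alkaline phosphatase >1.5x | none | Yes, any subject |
| ALT/AST >3x with bilirubin >1.5x or >2x | both of the above | Only with hepatic involvement and Gilbert's together |
| QTcF >450, >480, >500 msec | none | Yes, any subject |

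**2. Which ULN.** Protocol 7.6.4 has these tests done at local laboratories. SAP Appendix E lists fixed ranges (upper limit 30 U/L for AST, 40 U/L for ALT), and the SAP does not say which set defines the multiples. With an assumed local AST ULN of 40 U/L, the entry limits on the Appendix E range become:

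- 2.5 x 40 / 30 = 3.33x
- 5 x 40 / 30 = 6.67x

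In that case the 3x row could be met at entry without liver involvement, and the 5x row with it. The result in step 1 for the 5x row therefore depends on a choice that the SAP leaves open.

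**3. Possible size.** The plan states no figure for these counts and no baseline prevalence, so there is nothing to reproduce and everything here except the denominator is assumed. The denominator is the planned 60 + 63 = 123 DLL3 high subjects (Protocol synopsis). The safety population may be larger.

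Let *s* be the share already above a limit at baseline, assumed still above it post-dose, and *t* the true new incidence among the rest. Without a baseline condition:

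counted incidence = s + (1 - s) x t

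For AST/ALT above 3x, assume 20 to 60% with hepatic involvement and 5 to 20% of those above 3x at baseline:

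- low: s = 0.20 x 0.05 = 1%, and 123 x 0.01 = 1.2 subjects
- high: s = 0.60 x 0.20 = 12%, and 123 x 0.12 = 14.8 subjects

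With t = 5%:

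| s | Calculation | Shown | With baseline condition |
|---|---|---|---|
| 1% | 0.01 + 0.99 x 0.05 | 6.0% | 5% |
| 4% | 0.04 + 0.96 x 0.05 | 8.8% | 5% |
| 8% | 0.08 + 0.92 x 0.05 | 12.6% | 5% |
| 12% | 0.12 + 0.88 x 0.05 | 16.4% | 5% |

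For QTcF above 450 msec, an assumed baseline prevalence of 2 to 15% gives 123 x 0.02 = 2.5 to 123 x 0.15 = 18.4 subjects already above the limit.

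**4. Whether other tables already answer this.** The SAP plans change from baseline for chemistry, a chemistry shift table from baseline to maximum CTCAE grade (Table 14.4_1.2), and QTcF increases from baseline. The shift table treats one analyte at a time, so it cannot give baseline status for the combined ALT/AST-plus-bilirubin rows or the Hy's Law listing. The QTcF increase rows do not show how many subjects above 450, 480 or 500 msec were there before dosing.

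**The case against.** The strongest reply is that the plan already uses baseline and that the threshold rows are a deliberate, inclusive display beside it. Much of this stands, and it rules out several stronger readings.

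- *Baseline is ignored.* Not so. A subject with a high but unchanged QTcF falls in none of the increase rows, and a subject who stays at 4x ULN shows no shift in CTCAE grade. The gap is confined to the absolute counts.
- *All four AST/ALT rows are inflated.* Under a common ULN only the 3x row is, and only through subjects with hepatic involvement.
- *A doubling from a high baseline would be invisible.* Under a common ULN, a subject who starts above 3x and doubles passes 6x and enters the 5x row, where nobody within the entry limit can be at baseline. The table would show it.
- *The SAP dropped a protocol analysis rule.* Protocol 7.6.1.7 does refer to "2-fold increases above baseline values for subjects with elevated values before drug" exposure, but as a trigger for close observation. It is not an analysis definition, and Protocol 9.2.9.3 plans no baseline-relative liver count.

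It is also fair that the combined rows can be met at entry only by a subject with both conditions, that the Hy's Law output is a listing of potential cases and not a rate, and that SAP 7.7 plans no formal safety inference. The SAP attributes its liver categories to a regulatory guidance. That source is not available here, and the point does not rest on any departure from it.

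The reply does not show that any planned output separates the affected absolute counts by baseline status.

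**Conclusion.** The point holds in a limited form. As written, the AST/ALT 3x, bilirubin, alkaline phosphatase, combined liver and absolute QTcF rows can include subjects who were over the limit before dosing, and the period definition does not exclude pre-dose values. The bias is upward and affects descriptive safety tables only. No primary endpoint or decision rule changes.

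The size is not known from the documents. The range of about 1 to 15 of 123 subjects for AST/ALT above 3x, and 2 to 18 for QTcF above 450 msec, rests on assumed prevalences. A reader might take these as estimates of overcounting in this trial, but the documents do not support that use. The finding that the 5x, 10x and 20x rows are unaffected rests on a common ULN, which the SAP does not state. The change is worth making because the baseline data are already collected and the cost is small.

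**What to change.** In SAP 7.7.2 and 7.7.4:

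1. State that only post-dose values count towards the threshold rows and the potential Hy's Law listing.
2. For each affected threshold, report subjects at or below it at baseline who exceed it post-dose, with that group as the denominator. Put subjects already above it at baseline in a separate row. This covers AST/ALT 3x, bilirubin 2x, alkaline phosphatase 1.5x, both combined rows, and QTcF 450, 480 and 500 msec.
3. Show baseline AST, ALT and bilirubin beside the qualifying values in Appendix 16.2_8.1.
4. State whether local or Appendix E upper limits define the multiples. If Appendix E is used, apply the same split to the AST/ALT 5x row.

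The cost is a few extra rows in Tables 14.4_4.1 and 14.3_6.1, some columns in one listing and two clarifying sentences. No new data are needed.

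### SAP 7.7.2 pairs transaminase and bilirubin elevations on unscheduled or repeat tests only within one assessment and sets no window across draws, so some subjects crossing both thresholds are left out of the potential Hy's Law listing

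*SAP*

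**What the plan says.** SAP 7.7.2 (Laboratory Tests) plans separate summaries of AST/ALT elevations and of total bilirubin above 2xULN. It also plans a combined row, AST or ALT above 3xULN with total bilirubin above 1.5xULN or above 2xULN, and a listing of potential Hy's Law cases, described as "subjects with AST or ALT >3 xULN in combination with bilirubin >2 xULN". That description is per subject and has no timing condition.

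The next sentence adds one. It lets tests done outside the schedule count towards these evaluations, on the condition that they do so "with elevations of AST or ALT in combination with total bilirubin at the same unscheduled or repeat assessment". Nothing is said about how two scheduled visits are paired, or how a scheduled draw is paired with an unscheduled repeat.

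Protocol 7.6.1.7 (Potential Drug-Induced Liver Injury) builds its definition from separate limbs. The first reads "ALT or AST elevation > 3 times (3X) upper limit of normal (ULN); AND" and the second "Total bilirubin > 2X ULN, without initial findings of cholestasis (elevated serum alkaline phosphatase), AND". A third limb excludes cases with another evident cause. No limb requires the elevations to be on the same draw. The same section says that a transaminase rise above 3xULN "should be followed by repeat testing within 48-72 hours of all four of the usual serum measures", and gives the purpose of that repeat: "ALT, AST, alkaline phosphatase, and total bilirubin) to confirm the abnormalities and to determine if they are increasing or decreasing". It then describes two or three tests a week under close observation.

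**The concern.** The protocol follows liver tests over successive draws. The SAP sentence looks within one draw. Bilirubin can cross its threshold after the transaminases have begun to fall, or before they rise. In that case the two elevations sit on different draws, and the SAP rule does not join them.

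The listing is a mechanical screen for a rare and serious event. It needs no investigator to recognise the pattern or attribute it to drug. A subject who crosses both thresholds on neighbouring draws is one a safety reviewer would want to look at, and the rule as written can leave that subject off the list.

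There is also an ambiguity. Scheduled draws have no stated pairing rule, so a programmer could pair them at subject level while holding repeats to the same assessment. The same biochemical course could then be listed or not according to how the visit was labelled.

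**Working it through.** There is no sample size, power or error rate to reproduce. The check applies two pairing rules to hypothetical pairs of draws.

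**Inputs from the documents**
- Thresholds: AST or ALT above 3xULN, total bilirubin above 2xULN (SAP 7.7.2; the same cut-offs are in Protocol 7.6.1.7).
- Repeat: 48-72 hours after the index draw, with AST, ALT, alkaline phosphatase and total bilirubin measured together (Protocol 7.6.1.7).

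**Rules**
- Same-assessment: listed if at least one draw has transaminase > 3 and bilirubin > 2. I apply this to a scheduled index draw followed by a repeat, because the SAP states no other pairing rule.
- Across-draws: listed if some draw has transaminase > 3 and some draw, the same or another, has bilirubin > 2.

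**Illustrative values** (in xULN; transaminase is the higher of AST and ALT; these are not trial data)

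| Pair | Index draw: transaminase / bilirubin | Repeat: transaminase / bilirubin | Same-assessment | Across-draws |
|---|---|---|---|---|
| A | 5.0 / 1.2 | 4.0 / 2.4 | listed | listed |
| B | 3.6 / 1.2 | 2.8 / 2.4 | not listed | listed |
| C | 4.0 / 2.3 | 2.5 / 1.9 | listed | listed |
| D | 2.5 / 2.3 | 3.5 / 1.8 | not listed | listed |

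- A: on the repeat, 4.0 > 3 and 2.4 > 2, so the late bilirubin rise is caught.
- B: the index draw fails on bilirubin (1.2 ≤ 2) and the repeat fails on transaminase (2.8 ≤ 3). No single draw meets both.
- C: the index draw meets both.
- D: the index draw fails on transaminase (2.5 ≤ 3) and the repeat fails on bilirubin (1.8 ≤ 2).

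At the SAP's lower bilirubin cut-off of 1.5xULN, D enters the combined row through its repeat (3.5 > 3 and 1.8 > 1.5), but B still does not.

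The rules therefore differ exactly when both thresholds are crossed in the subject but on no single draw. For a bilirubin rise first seen on the repeat, both AST and ALT must be at or below 3xULN on that repeat, or have no result. One of them staying above 3xULN is enough for the subject to be listed.

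**The case against.** The strongest reply is that the gap is narrow and other outputs cover it.

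- **The repeat is paired by design.** All four tests are drawn together, so a reader who inferred that the repeat is itself a blind spot would be wrong. A subject is lost only under the condition above, and any later draw that crosses both thresholds restores the subject. This stands and limits the point.
- **The subject does not vanish from the report.** The separate AST/ALT and bilirubin summaries remain, as does the chemistry listing (SAP Appendix G, Appendix 16.2_8.3.1). Protocol 7.6.1.7 also makes potential DILI reportable as a serious adverse event. This stands too, with limits. The summaries do not link the two tests within a subject, and the chemistry listing leaves the reader to find the pair by hand. The adverse event route depends on the investigator's recognition and judgement of cause. Routine reporting also ends 30 days after the last dose (Protocol 7.6.1.3), while end-of-treatment chemistry is due no earlier than day 42 − 3 = 39 (Protocol 6.4). After day 30, only events judged treatment-related are reported.
- **The SAP is not narrower than the protocol in every respect.** The listing applies neither the cholestasis limb nor the other-cause limb, so it is broader there. On timing the protocol is silent, and silence does not prescribe any-time pairing. It is fair to say only that the protocol has no same-draw condition and the SAP adds one.
- **Unlimited pairing would bring in unrelated events.** The initial treatment period can run to new anticancer therapy or the end of study (SAP 6). Entry allows AST/ALT up to 5xULN with hepatic involvement and bilirubin up to 3xULN with Gilbert's disease (Protocol 4.1). Peaks months apart could be joined. This stands, and it is the reason for a bounded window.

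**Conclusion.** The point holds as a small gap in a descriptive safety listing. Under the SAP's rule, a subject with AST or ALT above 3xULN on one draw and total bilirubin above 2xULN on another is absent from the above-2xULN combined row and the potential Hy's Law listing when no single draw crosses both.

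This assumes that the same-assessment sentence also governs a scheduled draw followed by a repeat. The SAP does not say so, and that silence is part of the defect.

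The number of subjects affected cannot be estimated. Routine chemistry falls on Days 1, 15 and 29 and at end of treatment, and a reader might infer from this spacing that the two peaks often fall on different draws. The documents give no data for that, and separate peaks alone do not lose a subject. They also do not support saying that a liver injury case would be missing from the study report altogether. No efficacy endpoint, stopping rule or formal inference is affected.

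**What to change.** Replace the same-assessment sentence in SAP 7.7.2 with one pairing rule for all draws: AST or ALT above 3xULN paired with total bilirubin above 2xULN across scheduled, unscheduled and repeat assessments, within a window fixed in advance. The documents give no basis for its length, so the sponsor must set it, and should state whether it runs in both directions so that bilirubin-first cases such as pair D are settled. Apply the same rule to the combined row.

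In the listing, show both dates, the baseline AST, ALT and bilirubin, and a flag for elevations on the same draw. The flag keeps the present rule's result visible.

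The cost is one SAP sentence and a small programming change, with no new data and no change to retesting or treatment. The downside is some extra subjects to review, including some with hepatic metastases or raised baseline values. The baseline columns and dates help to sort them.
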